2.0 LIST OF ABBREVIATIONS

AE	adverse event
ADR	adverse drug reaction
ALT	alanine aminotransferase
AST	aspartate aminotransferase
BA/CA	bone age/chronological age
BMD	bone mineral density
BMI	body mass index
CFDA	China Food and Drug Administration
CI	confidence interval
CMH	Cochran-Mantel-Haenszel
CPP	central precocious puberty
CRF	case report form
CRO	contract research organization
FAS	full analysis set
FDA	Food and Drug Administration
FSH	follicle-stimulating hormone
GCP	Good Clinical Practice
GGT	γ-glutamyl transferase
GnRH	gonadotropin releasing hormone
GnRHa	gonadotropin releasing hormone analogs
GPP	Good Pharmacoepidemiology Practices
ICH	International Conference on Harmonisation
IEC	independent ethics committee
IRB	institutional review board
ISPE	International Society for Pharmacoepidemiology
LH	luteinizing hormone
MedDRA	Medical Dictionary for Regulatory Activities
PMDA	Pharmaceuticals and Medical Devices Agency
QTc	corrected QT interval
RBC	red blood cell
SAE	serious adverse event
SAP	statistical analysis plan
SC	subcutaneous
SOC	system organ class
WBC	white blood cell
WHODRUG	World Health Organization Drug Dictionary

5.0 ABSTRACT

Title

An Observational, Retrospective Study to Evaluate Long Term Safety and Effectiveness of Leuprorelin in the Treatment of Central Precocious Puberty

Rationale and Background

Precocious puberty refers to appearance of secondary sexual characteristics in boys before 9 years and girls before 8 years [1]. Children with central precocious puberty (CPP) have premature secretion and release of gonadotropin releasing hormone (GnRH) in the hypothalamus, activating secretion of gonadotropin by the pituitary gland, promoting development of the gonads and secretion of sex hormones, resulting in development of internal and external genital organs and appearance of secondary sexual characteristics [1]. Treatment goals include hormonal suppression, cessation of development of secondary sex characteristics, halting or preventing menarche, and preservation of adult height [1][2]. If left untreated, children with CPP can also face psychological challenge resulting from premature physical maturation that contrasts with their immature emotional development [2].

GnRH analogs (GnRHa) have been the standard of care for CPP [1]. Continuous exposure to GnRHa desensitizes pituitary gonadotropin receptors and suppresses luteinizing hormone (LH) and follicle stimulating hormone (FSH) secretion [2].

Leuprorelin acetate (trade name: ENANTONE) is a GnRHa widely used in the treatment of CPP. It was approved for CPP indication in China in 1998 at the dose of 30-90 µg/kg body weight subcutaneously administration every 4 weeks. However, recent clinical studies demonstrated that administration of leuprorelin acetate at lower than 90 µg/kg body weight cannot achieve optimal pituitary desensitization in many patients. If incomplete suppression is operative during treatment, GnRHa administration may exacerbate disease progression and bone age increase, impairing long-term outcome [3]. The dose greater than 90 µg/kg body weight was recommended in CPP treatment guideline issued in 2010 by the Ministry of Health of China and Consensus on Diagnosis and Treatment of Central Precocious Puberty (2015) [4][5].

In 2013, China Food and Drug Administration (CFDA) approved the new dose of leuprorelin acetate at 30-180 µg/kg body weight, subcutaneous (SC), every 4 weeks [6]. The approval was based on results from the clinical trials of leuprorelin acetate conducted in US and Europe and a retrospective study in Japan [7][8]. There is a lack of safety and effectiveness data of leuprorelin acetate long term use in China. This retrospective, medical chart review study is designed to evaluate and compare descriptively the effectiveness and safety of high dose (≥ 90 µg/kg up to 180 µg/kg) and low dose (<90 µg/kg down to 30 µg/kg) leuprorelin acetate in China.

Research Question and Objectives

The goal of this study is to evaluate the safety and effectiveness of leuprorelin acetate in CPP treatment in China.

Objective 1: To describe the safety of high dose leuprorelin acetate (≥ 90 $\mu\text{g}/\text{kg}$ up to 180 $\mu\text{g}/\text{kg}$) and low dose leuprorelin acetate (< 90 $\mu\text{g}/\text{kg}$ down to 30 $\mu\text{g}/\text{kg}$) in CPP treatment of at least 9 continuous months of ENANTONE

Objective 2: To describe the long term effectiveness of high dose leuprorelin acetate (≥ 90 $\mu\text{g}/\text{kg}$ up to 180 $\mu\text{g}/\text{kg}$) and low dose leuprorelin acetate (< 90 $\mu\text{g}/\text{kg}$ down to 30 $\mu\text{g}/\text{kg}$) in CPP treatment of at least 9 continuous months of ENANTONE

Study Design

Observational retrospective medical chart review study.

Population

Patients with central precocious puberty treated with ENANTONE for at least 9 continuous months duration, initiated and received the last dose of ENANTONE treatment during the index period from 1 September 1998 to 30 September 2018 in multiple centers across China. Patients who were treated with other GnRHa (including generic leuprorelin acetate) after the 9-months treatment with ENANTONE can be enrolled into the study.

Outcomes

Primary Outcomes

- 1) Safety - Adverse events (AEs) and serious adverse events (SAEs) reported by physicians in the medical records (eg, incidence of any injection site reaction) during and after treatment with ENANTONE
- 2) Effectiveness - Regression or no progression in Tanner staging during and after treatment with ENANTONE

Secondary Outcomes

- 1) LH and FSH suppression to prepubertal level during and after treatment with ENANTONE
- 2) Estradiol or testosterone level suppression during treatment with ENANTONE
- 3) Decrease in the ratio of bone age to chronological age (BA/CA ratio) during treatment with ENANTONE

Additional Outcomes

- 1) Increase in predicted adult height during and after treatment with ENANTONE
- 2) Change from baseline in standard laboratory tests during and after treatment with ENANTONE
- 3) Incidence rate of polycystic ovarian syndrome during and after treatment with ENANTONE
- 4) Evaluation of the long term effect on reproduction
- 5) Change from baseline in bone mineral density (BMD) during and after treatment with ENANTONE
- 6) Change from baseline in body mass index (BMI) during and after treatment with ENANTONE

Data Sources

The retrospective study will be undertaken in China using the medical records of CPP patients from geographically distributed hospitals in both northern and southern China.

Study Size

Approximately 300 subjects (planned)

Data Analyses

A statistical analysis plan (SAP) will be prepared and finalized prior to completion of the data collection period. This document will provide further details regarding the definition of analysis variables and methodology to address all study objectives.

6.0 AMENDMENTS AND UPDATES

This document describes the changes in reference to the Protocol Incorporating Amendment No. 01.

The primary purpose of this amendment is to revise the objectives, outcomes and inclusion/exclusion criteria to allow patients who were treated with GnRHa other than ENANTONE after the ENANTONE treatment to be enrolled into the study, provided that they have been treated with at least 9 continuous months of ENANTONE during the index period. Also, the index period is extended by 1 year from the original plan to enable further enrollment of patients.

Number	Section of study protocol	Amendment or update	Reason
1	Section 1.1 Approval	Updated the signatories.	To reflect the latest team membership.
2	Section 4.0 Responsible Parties	Updated the contact information.	To reflect the latest team membership.
3	Section 7.0 Milestones	Updated the actual dates for start of data collection and public disclosure.	To reflect the latest study progression.
4	Section 9.0 Research Question and Objectives (a)	Revised the wording for Objectives 1 and 2.	To reflect the change in study population (as described in row #5 of this table).
5	Section 10.1 Study Design (a)	Revised the study population requirement.	To allow patients who were treated with GnRHa other than ENANTONE after the ENANTONE treatment to be enrolled into the study provided that they have been treated with at least 9 continuous months of ENANTONE during the index period.
6	Section 10.1 Study Design (a)	Added detailed description and diagram on the study design.	To clarify the definition of each study phase and time points.
7	Section 10.1 Study Design (a)	Extended the end of the index period from 30 September 2017 to 30 September 2018.	To allow further enrollment of patients into the study.
8	Section 10.1 Study Design (a)	Added detailed description on dose groups.	To clarify how the patients will be categorized into each dose group.
9	Section 10.2.1 Outcomes (a)	Redefined the Secondary Outcomes by re-categorizing Secondary Outcomes #4 to #9 in the original protocol into Additional Outcomes #1 to #6.	To clarify the priority of the outcomes.
10	Section 10.2.1 Outcomes (a)	Removed the Secondary Outcome # 10 (Injection site reaction during the treatment phase) in the original protocol.	The assessment of injection site reaction is included in the Primary Outcome #1 (Safety).

(a) Section 5.0 (Abstract) also revised accordingly.

Number	Section of study protocol	Amendment or update	Reason
11	Section 10.2.2 Variables to be Collected	New section created.	To clarify the types of variables to be collected.
12	Section 10.2.3 Variables Collected During Each Study Phase	New section created.	To clarify the variables to be collected during each study phase.
13	Section 10.4.1 Inclusion Criteria	Revised inclusion criteria #2, #3, #4 and #5.	To reflect the change in study population and index period (as described in rows #5 and #7 of this table).
14	Section 10.4.2 Exclusion Criteria	Revised exclusion criteria #1 and #2.	To reflect the change in study population (as described in row #5 of this table).
15	Section 10.7 Data Analysis	Revised the description of data analysis plan.	To reflect the change in study population (as described in row #5 of this table), and for clarification.
16	Section 10.7.1 Analysis Sets	Revised the definition of Per Protocol Set.	To reflect the change in study population (as described in row #5 of this table).
17	Section 10.7.3 Effectiveness Analysis	Revised the description of covariates on BMI analysis.	To revise typo.
18	Section 10.8.2 Protocol Deviations	Added description on protocol deviation rule.	To clarify that missing data for non-mandatory variables will not be handled as protocol deviation.
19	Throughout the protocol	Revised/edited texts (including grammatical and editorial changes).	For clarification purposes.

(a) Section 5.0 (Abstract) also revised accordingly.

7.0 MILESTONES

Milestone	Planned Date	Actual Date	Comments
Draft protocol to PRC	07 July 2016	07 July 2016	NA
Protocol approval	30 Sep 2016	10 Oct 2016	NA
Start of data collection	31 Dec 2016	24 Jun 2017	NA
End of data collection	30 Jun 2018	To be determined	NA
Public Disclosure	31 Oct 2016	13 Dec 2016	NA
Final study results	30 Sep 2018	To be determined	NA
Final report of study results	31 Dec 2018	To be determined	NA

8.0 RATIONALE AND BACKGROUND

Precocious puberty refers to appearance of secondary sexual characteristics in boys before 9 years and girls before 8 years [1]. Children with CPP have premature secretion and release of GnRH in the hypothalamus, activating secretion of gonadotropin by the pituitary gland, promoting development of the gonads and secretion of sex hormones, resulting in development of internal and external genital organs and appearance of secondary sexual characteristics [1]. Treatment goals include hormonal suppression, cessation of development of secondary sex characteristics, halting or preventing menarche, and preservation of adult height [1][2]. If left untreated, children with CPP can also face psychological challenge resulting from premature physical maturation that contrasts with their immature emotional development [2].

GnRHa have been the standard of care for CPP [1]. Continuous exposure to GnRHa desensitizes pituitary gonadotropin receptors and suppresses LH and FSH secretion [2].

ENANTONE is a GnRHa widely used in the treatment of CPP. It was approved for CPP indication in China in 1998 at the dose of 30-90 µg/kg body weight subcutaneously administration every 4 weeks. However, recent clinical studies demonstrated that administration of leuprorelin acetate at lower than 90 µg/kg body weight cannot achieve optimal pituitary desensitization in many patients. If incomplete suppression is operative during treatment, GnRHa administration may exacerbate disease progression and bone age increase, impairing long-term outcome [3]. The dose greater than 90 µg/kg body weight was recommended in CPP treatment guideline issued in 2010 by the Ministry of Health of China and Consensus on Diagnosis and Treatment of Central Precocious Puberty (2015) [4][5].

In 2013, CFDA approved the new dose of leuprorelin acetate at 30-180 µg/kg body weight, SC, every 4 weeks [6]. The approval was based on results from the clinical trials of leuprorelin acetate conducted in US and Europe and a retrospective study in Japan [7][8]. There is a lack of safety and effectiveness data of leuprorelin acetate long term use in China. This retrospective, medical chart review study is designed to evaluate and compare descriptively the effectiveness and safety of high dose (≥ 90 µg/kg up to 180 µg/kg) and low dose (< 90 µg/kg down to 30 µg/kg) leuprorelin acetate in China.

9.0 RESEARCH QUESTION AND OBJECTIVES

The goal of this study is to evaluate the safety and effectiveness of leuprorelin acetate in CPP treatment in China.

Objective 1: To describe the safety of high dose leuprorelin acetate ($\geq 90 \mu\text{g}/\text{kg}$ up to $180 \mu\text{g}/\text{kg}$) and low dose leuprorelin acetate ($<90 \mu\text{g}/\text{kg}$ down to $30 \mu\text{g}/\text{kg}$) in CPP treatment of at least 9 continuous months of ENANTONE

Objective 2: To describe the long term effectiveness of high dose leuprorelin acetate ($\geq 90 \mu\text{g}/\text{kg}$ up to $180 \mu\text{g}/\text{kg}$) and low dose leuprorelin acetate ($<90 \mu\text{g}/\text{kg}$ down to $30 \mu\text{g}/\text{kg}$) in CPP treatment of at least 9 continuous months of ENANTONE

10.0 RESEARCH METHODS

10.1 Study Design

10.1.1 Study Population and Design

This is an observational, retrospective study to evaluate long term safety and effectiveness of ENANTONE (leuprorelin acetate) in the treatment of CPP.

Approximately 300 patients with CPP, who were treated with ENANTONE for at least 9 continuous months, who initiated and received the last dose of treatment during the index period from 1 September 1998 to 30 September 2018, will be enrolled into the study. Patients who were treated with other GnRHa (including generic leuprorelin acetate) after the 9-months treatment with ENANTONE can be enrolled into the study. Within each site, sequential eligible patients will be enrolled until the site's patient quota has been reached. Medical records will be collected and reviewed.

[figure not shown]
Prior to ENANTONE treatment initiation, all relevant data (specified in Section 10.2.3.1), including data pertaining to the diagnosis of CPP will be collected at all available time points.

The **ENANTONE Treatment Phase** is the period during which patients were treated with at least 9 continuous months of ENANTONE. All relevant data (specified in Section 10.2.3.2) will be collected at all available time points.

The **Follow-up Phase** is the period after the ENANTONE Treatment Phase up to the day of last available follow-up data for the subject. All relevant data (specified in Section 10.2.3.2) will be collected at all available time points after the ENANTONE Treatment Phase. At a minimum, the data from the most recent time point available in the medical record should be included so as to include data on long term follow up of the subject. During the Follow-up Phase, a GnRHa Treatment Interval may apply to those patients who were treated with a GnRHa other than ENANTONE (either generic leuprorelin acetate or other GnRHa) for CPP; in this case, the dates of therapy with this other GnRHa should be noted in the case report form (CRF).

The study design is shown in [Figure 10.a](#).

Figure 10.a Overview of Study Design

(a) Baseline: First day of administration of ENANTONE.

(b) End of Follow-up: The day of last available follow-up data for the subject.

10.1.2 Exposure

During the ENANTONE Treatment Phase, patients should have received at least 9 continuous months treatment with ENANTONE. According to the dose of ENANTONE the patient first received at Baseline and the weight of the patient at Baseline, each patient will be categorized to either one of the following dose groups:

- Low dose group: subcutaneous injection of ENANTONE <90 µg/kg down to 30 µg/kg
- High dose group: subcutaneous injection of ENANTONE ≥90 µg/kg up to 180 µg/kg

10.2 Variables

10.2.1 Outcomes

Primary Outcomes

- 1) Safety –Adverse events (AEs) and serious adverse events (SAEs) reported by physicians in the medical records (eg, incidence of any injection site reaction) during and after treatment with ENANTONE
- 2) Effectiveness - Regression or no progression in Tanner staging during and after treatment with ENANTONE

Secondary Outcomes

- 1) LH and FSH suppression to prepubertal level during and after with ENANTONE
- 2) Estradiol or testosterone level suppression to prepubertal level during and after treatment with ENANTONE

- 3) Decrease in the ratio of bone age to chronological age (BA/CA ratio) during treatment with ENANTONE

Additional Outcomes

- 1) Increase in predicted adult height during and after treatment with ENANTONE
- 2) Change from baseline in standard laboratory tests during and after treatment with ENANTONE
- 3) Incidence rate of polycystic ovarian syndrome during and after treatment with ENANTONE
- 4) Evaluation of long term effect on reproduction
- 5) Change from baseline in BMD during and after treatment with ENANTONE
- 6) Change from baseline in BMI during and after treatment with ENANTONE

10.2.2 Variables to be Collected

The following variables may be collected and recorded on the CRF as are available in the subject's chart. At a minimum, data related to the primary and secondary endpoints should be collected. This includes data at time of diagnosis of CPP, at the beginning of the ENANTONE Treatment Phase, at the end of the ENANTONE Treatment Phase and at the most recent time in the Follow-up Phase.

10.2.2.1 Informed Consent

Each patient or, when applicable, the subject's legally acceptable representative must provide written informed consent before any study-required data are collected.

10.2.2.2 Patient Demographics

The date of birth, gender and family origin (North China/South China) of the patient will be recorded.

10.2.2.3 Disease History

The onset date of appearance of secondary characteristics and the CPP diagnosis date will be recorded.

10.2.2.4 BMD

The z-score for BMD and the anatomical site of measurement will be recorded. The BMD is typically determined using dual-energy X-ray absorptiometry, but BMD determined with any apparatus/mode is acceptable for collection.

10.2.2.5 Bone Age, Growth Rate and BA/CA Ratio

Bone age (years and presence of any abnormalities) and growth rate will be recorded.

BA/CA ratio will be calculated by the sponsor from the bone age and chronological age (derived from the date of birth, date when the X-ray was performed to assess bone age and the radiologic evaluation of bone age as available in the subject's chart all of which will be recorded in the CRF). The calculated BA/CA results will not be recorded in the CRF.

10.2.2.6 Height, Predicted Adult Height, Weight and BMI

Height, predicted adult height and weight will be recorded.

The predicted adult height is preferably derived by the Tanner-Whitehouse 3 method; where not possible, Bayley-Pinneau method or other methods are also acceptable.

The BMI will be calculated by the sponsor from the patient's weight and height recorded in the CRF. The calculated BMI results will not be recorded in the CRF.

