10.7.3 Effectiveness Analysis

Any inferential statistical analysis resulting in p-values will be reported for the purpose of identifying notable findings rather than any formal test of statistical significance. Unless specified otherwise, all point estimates will be estimated alongside a companion 95% CI.

The primary effectiveness outcome, percentage of subjects who have regression or no progression (ie, response to treatment) in Tanner staging at the end of the ENANTONE Treatment Phase will be analyzed using a Cochran-Mantel-Haenszel (CMH) test with sex as

strata variable and dose (high, low) as independent variable. The adjusted odds ratio and 95% CI will be provided from the CMH test along with two-sided p-value. The 95% CI for the percent will also be determined using Clopper-Pearson exact method, unadjusted for sex, will be provided for overall responder and for each sub-response (regression/ no progression) for all subjects and by sex. If the final data are incompatible with the above analyses, then another method, such as ordinary percentages with 95% CIs (example using Wald type CIs), may be used.

Additional CMH analyses with adjustment by other demographic variables may be performed where necessary. If the data in the treatment period permits, similar analysis as described above will be performed at year intervals from the initiation of treatment, ie, Year 1, Year 2, etc.

The above analyses methodology will be also applied to the following effectiveness outcomes, at the end of the treatment phase and at year intervals, if appropriate:

- Percentage of patients with LH suppression
- Percentage of patients with FSH suppression
- Percentage of patients with estradiol or testosterone level suppression to prepubertal level
- Percentage of patients with a decrease from baseline in the ratio of bone age to chronological age
- Percentage of patients with an increase from baseline in predicted adult height

Change from baseline for BMI at end of treatment phase will be analyzed. This analysis will also be performed at each year interval, as permitted by available data and where applicable, of the treatment phase.

The above analysis will be used for the following quantitative variables, with associated baseline value as covariate:

- Change from baseline in BMI during the follow up phase, at yearly intervals, with end of treatment phase BMI as baseline
- Change from baseline in BMD, at end of treatment phase and at yearly intervals

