### **7.8.3 Additional Efficacy Endpoint(s)**

Percent of patients with a change from baseline in the following parameters will be summarized in a similar manner as the above categorical secondary efficacy endpoint:

- Increase in predicted adult height during and after treatment with ENANTONE
- Change from baseline for BMI
- Change from baseline in BMD
- Change from baseline in patient height

For these and the other additional efficacy endpoints, descriptive statistics will be provided without inferential comparisons for the end of ENANTONE treatment phase and 3-month intervals and follow-up segments previously described.

- Increase in predicted adult height during and after treatment with ENANTONE
- Change from baseline in standard laboratory tests during and after treatment with ENANTONE
- Incidence rate of polycystic ovarian syndrome during and after treatment with ENANTONE
- Evaluation of long term effect on reproduction
- Change from baseline for BMI

- Change from baseline in BMD
- Change from baseline in patient height

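### The change in predicted adult height has no same-method condition, so when a child's prediction method differs between baseline and a later visit, the difference between methods is counted as change

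*Protocol*

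**What the plan says.** Protocol 10.2.2.6 sets out both what is collected and how it may have been obtained. The items are "Height, predicted adult height and weight will be recorded". On method, Tanner-Whitehouse 3 is preferred, but "where not possible, Bayley-Pinneau method or other methods are also acceptable". Nothing asks for one method per child, and the method is not a listed data item. Protocol 10.2.2.4, by comparison, does capture a descriptor of the measurement for bone mineral density: "The z-score for BMD and the anatomical site of measurement will be recorded".

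Bone age, which feeds a height prediction, is treated like predicted adult height. Protocol 10.2.2.5 says "Bone age (years and presence of any abnormalities) and growth rate will be recorded", with no reading method listed.

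For analysis, Protocol 10.7.3 names "Percentage of patients with an increase from baseline in predicted adult height". SAP 7.8.3 opens its list with "Percent of patients with a change from baseline in the following parameters will be summarized in a similar manner" and gives the item as "Increase in predicted adult height during and after treatment with ENANTONE"; the same item appears again among the descriptive summaries. Neither document sets a minimum gain, names a prediction method for the analysis, or splits results by method.

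**The concern.** Two prediction methods can give different adult heights for the same child on the same day. A change score is meaningful only if baseline and later value are on the same scale. The plan allows several scales, does not ask which one was used, and counts any rise above zero as an increase.

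Preserving adult height is one of the treatment goals in Protocol 8.0, and predicted adult height is the listed outcome that speaks to it most directly, since measured height rises in any growing child. SAP 7.13 drops the Cochran-Mantel-Haenszel comparison of dose levels, and SAP 7.8 presents efficacy by sex without inferential comparison. The result is therefore a before-after summary with no comparator in which a method artefact could cancel. Protocol 13.0 intends the study results for the regulator.

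**Working it through.** The documents give no figure for predicted adult height (no expected rate, SD, offset or switching rate), so there is nothing of the plan's own to reproduce. The check has two parts.

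**1. Following the rules as written**

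- Collection (Protocol 10.2.2.6): a value from Tanner-Whitehouse 3, Bayley-Pinneau or another method is accepted; the method is not listed.
- Baseline (SAP 7.1.1): the latest available value before ENANTONE starts, within 93 days for CPP variables, whatever the method. Follow-up has its own baseline, also with no method condition.
- Change (SAP 7.1.1): later value minus baseline, set to missing only if one of the two is missing.
- Choice of record (SAP 7.1.3): the value closest to the target day. Several numeric values on one day are averaged, so two predictions by different methods on one day would be blended.
- Response (Protocol 10.7.3, SAP 7.8.3): any increase.

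No step stops a mixed-method pair. Write c for the change that one method would have shown and d for the offset between methods:

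- observed change = c if the method is constant;
- observed change = c + d if the method changes after baseline.

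A constant method cancels within the child. A switch always shifts the change by d, but the increase status reverses only if d is opposite in sign to c and larger in absolute size.

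**2. Illustration of size (every input assumed)**

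Let μ be the mean within-method change and d the offset, both in SDs of that change, and let s be the share of children whose method changes, all in the same direction:

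% with increase = (1 − s) × Φ(μ) + s × Φ(μ + d)

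For a downward offset, use −d. The range taken is s = 0.10 to 0.30 and d = 0.5 to 2.

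No true mean change (μ = 0; 50.0% without switching):
- s = 0.10, d = 0.5 upward: 0.90 × 0.500 + 0.10 × 0.691 = 51.9%; downward 48.1%.
- s = 0.30, d = 2 upward: 0.70 × 0.500 + 0.30 × 0.977 = 64.3%; downward 35.7%.

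True mean gain of 0.5 SD (69.1% without switching):
- upward 70.6% to 78.2%; downward 67.2% to 50.4%.

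The mean change shifts by s × d, from 0.10 × 0.5 = 0.05 SD to 0.30 × 2 = 0.6 SD.

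If switches split equally in both directions, the effect cancels when μ = 0. With μ = 0.5, s = 0.30 and d = 2 it does not cancel fully: (78.2 + 50.4) / 2 = 64.3%, against 69.1%.

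For scale, with 100 children (SAP 6.0) the Clopper-Pearson 95% interval is 39.8% to 60.2% around 50% and 60.0% to 78.8% around 70%, a half-width of roughly 10 points. The illustrated shift at μ = 0 runs from 1.9 to 14.3 points. The interval does not reflect it.

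**The case against.** The case for leaving the plan alone has real force.

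- *Switching within a child is not shown.* A reader might infer from charts covering 1998 to 2018 at eight facilities that mixed pairs are common. That spread describes variation between children and sites. A child followed with one method throughout is unaffected, and the documents say nothing about how often methods change. This stands.
- *Pooling is not stated.* The SAP nowhere says that it combines methods. This follows only from having one variable, one percentage and no method condition. As a reading of the rules it holds; as a statement of intent it would not.
- *The size is assumed.* Offset, SD, switching share and common direction are all assumed. The low end is small beside the sampling error, and opposing switches offset each other wholly or in part. A reader might infer that the reported percentage is inflated; the documents give no direction.
- *The outcome ranks low.* It is an additional outcome (SAP 5.3), summarised descriptively. Eligibility does not require it (Protocol 10.4.1), and the minimum data cover only primary and secondary endpoints (Protocol 10.2.2). Measured height and the bone-age ratio are analysed as well. This stands and limits the importance of the point.
- *BA/CA is not a clean model, and central derivation is not a cure.* It is tempting to say that the sponsor's own calculation protects BA/CA and that predicted adult height should simply follow. Under Protocol 10.2.2.5 the sponsor only forms the ratio; the bone age is the chart reading. One formula for predicted adult height would carry the same unrecorded differences in bone-age reading. Recalculation therefore belongs in a sensitivity analysis.
- *The CRF is not among the documents* and may already capture the method. That affects the cost of the fix. It does not supply the missing analysis rule.

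The gap in the analysis rules survives all of these.

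**Conclusion.** The point holds in a limited form. Followed as written, the plan adds any within-child difference between prediction methods to the change in predicted adult height, and it can turn a non-increase into an increase or the reverse. This rests on the text of Protocol 10.2.2.6 and SAP 7.1.1, 7.1.3 and 7.8.3, and on no outside figure.

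Frequency, size and direction are unknown. Under the assumed range (10% to 30% switching one way, offset 0.5 to 2 SD, no true mean change) the percentage moves by about 2 to 14 points. That shows what could happen; it does not estimate what did. It would be wrong to conclude that every switch counts as a gain or a loss, that the result is biased in a known direction, or that primary or secondary conclusions are at risk through this outcome. The point deserves action because an inexpensive analysis rule closes the gap.

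**What to change.** 1. Record the prediction method, and the bone-age reading method, wherever the chart states them, if the CRF does not already do so.
2. In SAP 7.8.3, compute the change and the percentage with an increase only from pairs in which baseline and later value used the same method. Apply this to the treatment phase and to follow-up with its own baseline.
3. Add an exception to SAP 7.1.3 so that same-day predictions from different methods are not averaged.
4. Report the number of pairs with differing or unknown method separately, beside the number analysed.
5. As a sensitivity analysis, recalculate predicted adult height with one method named in advance, from recorded height, bone age, chronological age and sex. State that this does not remove differences in how bone age was read.

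**Cost.** SAP wording and modest programming. Fewer children will be evaluable, possibly many fewer if charts seldom name the method, so the denominator must be shown. If the CRF lacks the field, sites must go back to the charts, and additions after submission go through the investigator-signed Data Clarification Forms of Protocol 10.6.1. The recalculation also loses visits without a height near the X-ray date.
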